Regression analyses will be used to assess relationships between progression to acute bacterial sinusitis, demographic variables (including age, gender, attendance at daycare, family or personal history of asthma, pets, etc.), season and gross metrics of bacterial community composition (richness, evenness, and diversity indices) as well as the relative abundance of all taxa detected (including sinopathogens), to determine if these variables are related to specific features of the nasopharyngeal microbiota. A term will be included to account for the paired structure of the data. For each of the continuous predictors, a difference in the mean values between the acute bacterial sinusitis group and the control group equal to 50% of the variability of that predictor will give us greater than 80% power to find a significant effect of the predictor. For predictors which take values of yes or no (such as presence of a sinopathogen), we will have 80% power to detect the difference between the percent of sinopathogens present equal to 55% for the acute bacterial sinusitis group and 30% for the control group.

PhyloChip outcomes including richness, evenness and diversity indices of the nasopharyngeal microbiome sample obtained during each of the 50 episodes of acute bacterial sinusitis will be compared to those obtained during the most recent surveillance period by using paired t-tests. Differences in specific taxon abundance in these two samples will be determined by paired t-test and adjusted for false discovery.

Correlation analysis of the abundance of each individual taxon against that of key sinonasal pathogens (both bacterial and viral) will also be performed to determine relationships between these species and relative abundance of all other taxa detected. Hierarchical cluster analysis will be used to display similarity of microbiota among nasopharyngeal samples.

The pilot stool sample size is based on the base sample size of 12 per group when no prior information is available (Julious, 2005). We propose to double that number to ensure enough samples over the seasonality of the one year enrollment. This feasibility is based on our average enrollment of 7 subjects per month and if 20% join the sub-study (1-2 per month), enrollment would take about 12 months including family members.

Innovation **This study will address numerous gaps in our knowledge of secondary bacterial infections (acute bacterial sinusitis, and also acute otitis media and bacterial pneumonia) of viral URI.** First, due to limitations in previously available viral diagnostics and a lack of stringent clinical criteria for acute bacterial sinusitis, there have been no previous studies to determine the incidence of acute bacterial sinusitis as a complication of viral URI. We propose to collect specimens quarterly during periods of health, and then multiple times during the course of an illness in order to gather a unique data set to define the relationship between viral URI and bacterial sinusitis. The high-throughput multiplex PCR-based viral diagnostics are ideal for identification of respiratory viruses in the over 5000 specimens to be collected. Second, no studies have been conducted to identify specific viral antecedents of acute bacterial sinusitis in children. Third, despite the immense clinical importance of respiratory infections in children, the nasopharyngeal microbiome of the child, whether in health, after exposure to common respiratory viruses, or during acute sinusitis, is virtually unknown. **Using culture-independent approaches will allow us to better understand the ecology of the microbiota of the nasopharynx and how these relationships are altered during viral infection or bacterial sinusitis.** In fact, to date there have been no previous studies of the nasopharyngeal microbiome in children.

In addition to the major knowledge gaps that we have identified in the preceding paragraph, this unique data set will allow us to address other outstanding questions of clinical importance including:

- a) Are children who experience closely spaced viral URIs more likely than those who experience infrequent URIs to develop acute bacterial sinusitis?
- b) What proportion of children with a first episode of acute bacterial sinusitis experience multiple episodes of sinusitis in one year?
- c) What proportion of episodes of acute bacterial sinusitis actually represent sequential episodes of very closely spaced viral URIs? (virus identified during episode of sinusitis is different from virus identified during the beginning of the respiratory illness)
- d) What proportion of episodes of acute “severe onset” bacterial sinusitis is caused by viral infections?
- e) Are children with asthma more likely than children without asthma to progress to acute bacterial infection after an antecedent acute viral URI?

Existing Challenges

a) Collection of representative samples of nasal mucus and nasopharyngeal specimens repeatedly from young subjects. To encourage families to report all respiratory illnesses, even mild URI, \$25 will be provided for each illness visit. To maintain participation in the study, the method of acquiring respiratory samples must be acceptable to young children and not uncomfortable yet retain sensitivity and be useful for processing by culture-independent approaches. Various methods were considered but the following were deemed the best on the basis of past experience and review of the literature.

Collection of nasal mucus. Study subjects will collect samples of their own nasal mucus using a “nose-blowing” technique.²⁹ The “nasal blow” procedure will be taught to the study participants at the first study visit. Briefly, participants spray saline into one nostril, occlude the other one, and then blow the nose into a “baggie”. The procedure is repeated on the other side. Viral transport medium is added to the baggie which is then sealed and placed into a container in the freezer. To model effects of storage conditions on detection of rhinoviruses (HRV), we conducted preliminary experiments in which samples of low-dose HRV (10^2 particles per sample) were stored in plastic self-locking bags in the saline/gelatin mix at either room temperature, 4°C, or -20°C. Specimens at all temperatures did not lose signal in our PCR-based diagnostic assays for at least 5

weeks (which was the duration of the test). These techniques have been used extensively in our previous pediatric studies and are extremely well tolerated when used for routine sampling.²⁹

Collection of nasopharyngeal specimens for conventional culture and microarray analysis.

Nasopharyngeal swab samples for assessment of the nasopharyngeal microbiome and standard bacterial cultures will be collected at enrollment, during surveillance visits and at the first and a subsequent visit of each URI episode using flocked swabs (Copan Diagnostics, Inc. Murrieta California). The soft strands of nylon on the swab result in tremendously improved patient comfort and efficiency in specimen collection. The velvet brush-like texture collects liquid by capillarity and rapidly and efficiently dislodges cells, providing an optimal approach to sampling for this study. First, the swab is inserted into the nostril along the floor of the nasal cavity until the posterior wall is reached. The swab is held in place for 2-3 seconds while rotating gently. The swab (cut by sterile scissors) will be placed immediately into 2 ml of RNALater in preparation for PhyloChip processing. Tubes will be stored at 4 °C overnight prior to storage at -80 °C.

We have extracted DNA from 8 nasopharyngeal swab samples; total DNA concentrations ranged from ~650 ng to 2.3 µg. To determine the relative ratio of microbial and mammalian DNA retrieved, we also performed 16S rRNA and β-actin q-PCR analysis of all 8 samples. A ratio of approximately 1:100 bacterial to mammalian DNA was observed across the samples, which is very similar to what we have previously observed in bronchial brush samples of asthmatic patients. Finally, to determine whether sufficient bacterial DNA was present in these samples to produce sufficient 16S rRNA amplicon to analyze by PhyloChip, we performed 12 PCR reactions across a gradient of annealing temperatures using 30 ng of total DNA as template, as we do routinely for all samples to be analyzed by array. The lowest concentration of pooled 16S rRNA product was 732 ng, suggesting that all samples could be analyzed by PhyloChip at a standard concentration of 500 ng. In previous studies we have successfully profiled communities using as little as 100 ng of amplified PCR product per sample. These data show that nasopharyngeal swab samples provide sufficient material for bacterial community profiling by the 16S rRNA PhyloChip.

b) Overcoming variability of the nasopharyngeal microbiome. Characteristics of nasopharyngeal colonization vary according to a variety of factors including attendance at day care, season, age, recent illness, socioeconomic status, etc¹⁰. To overcome this variability and still have a valuable baseline specimens that will permit comparison with an illness specimen, we will obtain surveillance specimens at entry and 4 other times. The specimens obtained closest in time preceding the episode of URI will be used as the baseline comparator.

c) Overcoming frequency of asymptomatic colonization with respiratory viruses. To interpret relationships between respiratory viruses and clinical illness, it is important to consider that respiratory viruses are detected in children without respiratory symptoms. The frequency of asymptomatic infection varies with age: viruses are detected in ~15% of healthy school-aged children and up to 31% of healthy infants.^{29,30} We will perform surveillance viral diagnostics on nasal wash samples at entry and 4 other occasions to estimate the seasonal frequency of asymptomatic infections for our study population; this information will be used as a reference point in analyses of viral infections during periods of illness.

d) Definition of Sinusitis: The 3 clinical presentations of sinusitis detailed in C.3.c above are widely accepted by 5 national societies: the American Academy of Allergy, Asthma and Immunology, the American Academy of Otolaryngic Allergy, the American Academy of Otolaryngology – Head and Neck Surgery, the American College of Allergy, Asthma, and Immunology, and the American Rhinologic Society.¹⁷ The American Academy of Pediatrics and the Infectious Diseases Society of America are including these presentations in their new guidelines (in press and PI is an author). In 4 clinical studies it has been shown that by using these stringent criteria, sinusitis is diagnosed in only 7-8% of respiratory infections presenting to the pediatrician.^{3,4,6,7}

e) Feasibility of enrollment, follow-up and Phylochip analysis. Both the principal investigator and the co-investigators have conducted several longitudinal studies over several years of large numbers of participants (daycare, asthma, birth cohort)^{2,29,30}. Subjects were recruited from the same practice that is participating in this study. The use of experienced coordinators and tested strategies for retention has led to excellent rates of

participation and retention in these studies. For example, the COAST cohort had 90% retention from prenatal enrollment to age 6 years³⁰ and the 1-year RhinoGen study (which includes recurrent sampling of nasal secretions, 400 participants) has an 85% rate of retention and full participation with study procedures (unpublished data). In addition, serial nasopharyngeal cultures as proposed in this study were performed by Revai et al with only 10% attrition.³¹ The practice associated with the University of Wisconsin Hospital and Clinics, has an eligible population of nearly 2500 children; we do not anticipate any difficulty in recruiting patients to this study. We estimate that children will have an average of 5 infections/year and 4 surveillance visits when asymptomatic in addition to the entry visit. The study visits and procedures are designed to minimize participant burden and discomfort. [name] has extensive expertise in translational microbiome studies^{15,32-35} and PhyloChip analyses of a variety of clinical samples, including those from adult patients with CRS (see preliminary data). Her group has acted as beta-testers for the G2 16S rRNA PhyloChip and helped develop and optimize the sample processing and statistical approaches described in **3d and e**. The study investigators have the extensive experience and expertise to successfully conduct this study.

Future Uses

We will be storing all data collected from the study and the material leftover from the nasal samples for potential future infectious disease research such as sinusitis. We also will be maintaining the master key linking the samples to identifiable information. The data will be maintained indefinitely on the Department of Pediatrics password-protected server and the master key will be stored in a separate folder on the server. The nasal samples will be maintained indefinitely in a -80 freezer located in the H4/4 pediatric lab space. Subjects may withdraw the data and samples by contacting the research staff.

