2. To compare children who develop acute bacterial sinusitis to children who recover spontaneously with regard to the characteristics of the nasopharyngeal microbiome (both gross features of community composition e.g. diversity, as well as the relative abundance of specific taxa). These comparisons will include samples obtained during the most recent surveillance visit, samples obtained during the acute URI and samples obtained when either a sinus infection has been confirmed or the subject has recovered spontaneously.

The secondary objective of the stool sample sub-studies are:

1. To determine the relationship, if any, between changes that occur in the nasopharyngeal microbiome and the fecal microbiome in the sub-cohort of subjects, and in the index subject and household family members, over time and with respiratory infections.

2. Timeline for conduct of study: There was a 3 month run-in period for IRB approval and training of personnel. The goal is to enroll nine patients per month (over 40 months). Each patient will be followed for 12 months; final follow-up will be completed at month 55. Enrollment began in February, 2012 and is ongoing. To date, 242 subjects have been enrolled. The average enrolled per month is approximately 6.5.

Table 2. Timeline for Conduct of Study

	Year 1				Year 2				Year 3				Year 4				Year 5			
	Quarter				Quarter				Quarter				Quarter				Quarter			
	1	2	3	4	1	2	3	4	1	2	3	4	1	2	3	4	1	2	3	4
Protocol finalization	X																			
Obtain IRB approval	X																			
Hire and train personnel	X																			
Recruitment (n=360)		27	27	27	27	27	27	27	27	27	27	27	27	27	27	27	9			
Analysis																		X	X	X

3. Eligibility and enrollment:

Main Study: Children will be eligible to join this study if they are between ≥ 4 through < 8 years of age and are otherwise healthy (without upper respiratory symptoms to obtain baseline nose samples). Exclusion criteria include underlying conditions which would predispose them to the development of sinusitis including congenital or acquired immunodeficiencies, craniofacial abnormalities, cystic fibrosis, allergic rhinitis or a previous episode of chronic sinusitis. Children will be recruited from four large pediatric practices. Informed consent will be obtained from a parent or legal guardian. Enrollment is ongoing and may extend further than the initial proposed timeline.

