e) Study methods - processing and interpreting the PhyloChip data. Detection and quantification criteria for each taxon detected by the PhyloChip will be conducted as described previously using a positive fraction threshold of ≥ 0.90 .²¹ Statistical analyses using log-transformed fluorescence intensities will be performed in the R environment (www.R-project.org), using the ecological community analysis package *vegan* [version 1.16-1; (129)] to calculate metrics of bacterial community composition, including richness (number of bacterial types present), evenness (relative distribution of species in a community) and diversity (index based on both richness and evenness metrics). Bray-Curtis dissimilarity measures of ecological distance will be calculated before performing non-metric multi-dimensional scaling, a nonparametric ordination method that maps community relatedness based on species presence and abundance. This approach will be used to assess variability in bacterial community structure (particularly to examine if a distinct community composition is associated with differential sinusitis outcomes). Between-group differences (e.g. sinusitis vs no-sinusitis) in both gross community metrics (e.g. richness, evenness and diversity) as well as taxon abundance will be determined by two-tailed *t*-testing or ANOVA and adjusted for false discovery using *q*-values, as we have recently described.¹⁴ Taxa exhibiting *p*- and *q*-values < 0.05 , will be considered statistically significant. Correlation analysis of taxon abundance against that of key sinonasal pathogens (both bacterial and viral) will be performed using the *multtest* package available as part of the Bioconductor suite of analysis programs²² to determine relationships between these species and relative abundance of all other taxa detected. All data will be maintained on a secure server in the Department of Medicine at UCSF, only accessible to those individuals involved in the study. Sequence data generated by 454-pyrosequencing will be used to validate 16S rRNA PhyloChip findings as we have previously described.²³

[figure not shown]
f) Study methods – Conventional bacteriology of nasopharyngeal swabs. Half of the nasopharyngeal swab will be submitted for routine bacterial cultures to the CLIA certified microbiology laboratory of the University of Wisconsin Hospital and Clinics. The plates will be interpreted semi-quantitatively. Isolates of *S.*

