between these two groups demonstrated that compared to healthy individuals, patients with CRS exhibited dramatic microbiota perturbation characterized by significantly reduced bacterial richness ($p \leq 0.008$; Fig. 3A), evenness ($p \leq 0.001$; Fig 3B) and diversity ($p \leq 0.008$; Fig 3C). These observations were further supported by hierarchical cluster analysis which demonstrated that the majority of healthy subjects clustered in a single tightly-knit group, whose bacterial communities were phylogenetically distinct from patients with CRS, who exhibited clustering of samples into two distinct groups (Group I and Group II; Fig. 3D). This exploratory analysis confirmed that the composition of the sinus microbiota of healthy subjects is distinct from that of CRS. These diverse communities included known pathogenic members of the Pseudomonadaceae, Lachnospiraceae, Ralstoniaceae, Mycobacteriaceae and Helicobacteriaceae

ii. A novel etiology for Chronic Rhinosinusitis (CRS) identified using the 16S rRNA PhyloChip.

In addition to our recent PhyloChip-based study which was the first to demonstrate distinct, niche-specific bacterial communities in paired nasopharyngeal and oropharyngeal samples of healthy adult subjects,¹⁵ we have also examined the sinus microbiota of patients with CRS. Maxillary sinus samples (7 CRS and 7 healthy individuals) were profiled using PhyloChip. Comparative analysis of gross metrics of bacterial community composition

detected in both CRS patients with, and healthy subjects without, sinonasal symptoms. Thus, the mere detection of a suspected or known pathogen at a given niche does not automatically imply pathogenic activity and suggests that the composition of the microbiota at that site may play a large role in defining the activity of community members.

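### The plan assigns the question of whether overall community composition differs by sinusitis outcome to an NMDS map and names no test on the dissimilarities

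*Protocol*

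**What the plan says.** Section 4.e (processing and interpreting the PhyloChip data) plans Bray-Curtis dissimilarities followed by NMDS, which it describes as "a nonparametric ordination method that maps community relatedness based on species presence and abundance". It gives this step a question about outcome: "particularly to examine if a distinct community composition is associated with differential sinusitis outcomes".

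The same section sends between-group differences in richness, evenness, diversity and taxon abundance to "two-tailed *t*-testing or ANOVA and adjusted for false discovery using *q*-values", with taxa called significant when p and q are both below 0.05.

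Section 4.i (Data Analysis, Aim 2) sets 50 sinusitis cases against 50 uncomplicated URIs matched in calendar time. It relates progression to the gross metrics and all taxa by regression, with a term for the pairing. It also states: "Hierarchical cluster analysis will be used to display similarity of microbiota among nasopharyngeal samples".

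Primary objective 2 is "To compare children who develop acute bacterial sinusitis to children who recover spontaneously with regard to the characteristics of the nasopharyngeal microbiome". It specifies these as "both gross features of community composition e.g. diversity, as well as the relative abundance of specific taxa", at three sampling times: the latest surveillance visit, the acute URI, and confirmed sinusitis or recovery.

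**The concern.** The protocol asks a yes/no association question and answers it with a display method. Ordination places samples on a map without using the outcome. Whether two sets of points look apart is then the reader's judgement, with no stated chance of being wrong in either direction.

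The tests planned elsewhere answer neighbouring questions. Two groups of samples can share the same richness, evenness and diversity and still differ in which organisms are present. Taxon tests ask about one organism at a time. The difference between whole communities (beta-diversity) is what Bray-Curtis measures, and it is the one quantity in this set without a test. The map also takes no account of the case-control pairs.

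At stake is a sentence in the results saying that the communities were distinct, or were similar, on the evidence of a plot alone.

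**Working it through.** **1. Match each quantity to its planned analysis.**

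| Quantity compared by outcome | Planned method | Where | Test named? |
|---|---|---|---|
| Richness, evenness, diversity | t-test or ANOVA with q-values; regression with pairing term | 4.e, 4.i | Yes |
| Abundance of single taxa | The same, with p and q < 0.05 | 4.e, 4.i | Yes |
| Overall composition (Bray-Curtis) | NMDS | 4.e | No |
| Similarity among samples | Hierarchical clustering | 4.i | Not needed; display only, not tied to outcome |

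The text contains no PERMANOVA, ANOSIM, MRPP or fitting of outcome to the ordination. Only the third row has an outcome question and no test.

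**2. Stated figure.** The protocol gives no alpha, power or sample size for a whole-community comparison, so there is nothing to reproduce.

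**3. What a test on the planned matrix gives.** With N = 100 samples, squared distances d² and n_g = 50 per group:

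- SST = (sum of d² over all sample pairs)/100
- SSW = sum over the two groups of (sum of d² within group)/50
- F = (SST − SSW) / [SSW/(100 − 2)]
- share of variation explained by outcome = (SST − SSW)/SST
- p = (1 + number of permuted F ≥ observed F)/(1 + number of permutations)

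If labels are swapped only within the 50 matched pairs, there are 2^50 ≈ 1.1 × 10^15 possible relabellings, so the number of permutations is no constraint. The level holds if case and control are exchangeable within a pair when outcome has no effect.

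**4. Unpaired simulation.** Assumed inputs: 50 v 50 samples, 500 correlated taxa, five latent factors, and Benjamini-Hochberg standing in for q-values.

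| Scenario | Permutation test on Bray-Curtis | Any taxon significant after FDR adjustment |
|---|---|---|
| No difference (300 runs) | 4.7% | 4.3% |
| 0.4 SD shift in 30% of taxa (150 runs) | 59% | 79% |
| 0.25 SD shift in 50% of taxa (150 runs) | 35% | 36% |

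The Monte Carlo standard error in the first row is √(0.05 × 0.95/300) = 1.3 percentage points, so both null rates are compatible with 5%.

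**5. Paired simulations.** Two were run on assumed inputs.

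- Null rejection for the within-pair test was 7% (14/200) in one and 3.5% in the other (200 runs). With a standard error of √(0.05 × 0.95/200) = 1.5 points, both are compatible with 5%.
- When the permutations ignored the pairs, power was 0% in one and at most 1% in the other, so the restriction matters.
- They disagreed on power. In the first (1,000 taxa, pair-effect SD 1), the within-pair test beat paired FDR taxon tests for diffuse shifts (85% v 30% for 0.2 SD in half the taxa) and was close for a concentrated one (59% v 65% for 0.4 SD in 10%). In the second, it was similar for diffuse shifts and lower for concentrated ones.

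**6. Three sampling times.** Three tests at 5% each, if independent, give a chance of at least one false positive of 1 − 0.95³ = 1 − 0.857 = 14.3%. A Bonferroni level would be 0.05/3 = 0.0167.

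**The case against.** The strongest reply is that the objective does not depend on the map. The features that objective 2 names are gross metrics and taxa, and both are formally tested. If no taxon truly differs, any rejection is a false one, so false-discovery control at 5% also limits the chance of any taxon finding to about 5%. An error-controlled route to saying that composition differs therefore exists. This stands, and it limits the point to the dissimilarity analysis. It does not supply a test for the question that section 4.e gives to NMDS.

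A second reply is that the choice of permutation test belongs in a statistical analysis plan, which may exist but is not shown. That is fair in part. However, the protocol does more than stay silent: it fixes a descriptive method for an association question.

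Four stronger readings are tempting, and the protocol does not support them:

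- *Objective 2 as a whole lacks error control.* Its named components have two-tailed tests with q-values.
- *Outcome will be judged from hierarchical clustering.* The protocol uses clustering only to show similarity.
- *The calendar matching is ignored throughout Aim 2.* The regression has a term for it. The complaint applies to the ordination and, in section 4.e, to two-group tests that do not mention pairs.
- *The preliminary data show the team inferring from pictures.* Section 4.h.ii does say "This exploratory analysis confirmed that the composition of the sinus microbiota of healthy subjects is distinct from that of CRS", from 7 v 7 samples. But that work is labelled exploratory, comes from another study, and followed tests on richness (p ≤ 0.008), evenness (p ≤ 0.001) and diversity (p ≤ 0.008). FDR-corrected taxon tests came after it.

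**Conclusion.** The point holds in a narrow form. The protocol uses Bray-Curtis and NMDS to examine whether overall composition is associated with sinusitis outcome, and names no test on the dissimilarities. A whole-community claim would have no stated error rate. Gross metrics and single taxa are not affected.

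The size cannot be put as an error in a stated figure, because there is none. The gain from a test is a controlled 5% level and an estimate of the variation explained by outcome. A reader might also infer that it would detect more than the planned taxon tests. The simulations do not settle this: the ranking changed with the assumed number of taxa, spread of the shift and pair effect, none of which the protocol gives. The conclusion assumes that no document outside the protocol already names such a test.

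**What to change.** In sections 4.e and 4.i (Aim 2):

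- Test the outcome effect on the planned Bray-Curtis matrix by PERMANOVA (adonis in the vegan package already named), with permutations restricted within the 50 matched pairs. Report the share of variation explained with the p-value.
- Add a check of equal dispersion (betadisper), since a difference in spread can also produce a small p-value.
- Keep NMDS as a figure. Clustering needs no change.
- If the test is run separately for surveillance, acute and sinusitis/recovery swabs, name one sampling time as the main test or adjust for three.
- Present the result as a complement to the FDR-adjusted taxon tests, not a replacement.

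The cost is a few lines of analysis code and wording, with no new samples or assays. The protocol describes enrolment as ongoing, so at this version the wording could be set before the final plots are read.
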